9.3 Recording of target parameters

- Non-invasive MSOT measurements
- Collection of relevant clinical data from patient file
- Recording of the flow profiles of A. femoralis communis and A. poplitea using CCDS
- Recording of ABI before and after exercise
- Recording of the relative (until the first occurrence of pain) and absolute walking distance (until the stopping due to pain)
- Recording of the maximum walking distance in the 6-minute walk test
- Recording of the subjectively perceived maximum walking distance in everyday life
- Recording of the currently perceived PAD-specific quality of life (VASCUQOL-6 questionnaire)
- Recording of the radiological severity of the disease (MRA, CTA, DSA)
[If angiographic imaging is already available due to routine diagnostics independent from this study.]

9.4 Total duration of the study

According to the expected required number of study participants, the expected total duration of the study until the inclusion of the last study participant is approximately six months. Participation in the study is approximately 90 minutes per study participant. Only one examination is required per patient.

10 Risk-benefit analysis

10.1 All study related risks

Based on the classification criteria for medical devices (Directive 93/42/EEC, Annex IX), the iThera Medical opto-acoustic system corresponds to Class IIa:

- active diagnostic device
- non-invasive
- temporary application (<60 min)

A CE certification is available for this research device (current type designation according to the label: Acuity Echo).

Adherence to energy limits

Laser safety and maximum radiation dose for exposure to laser pulses is regulated in the ANSI and IEC 60825 laser standards. The MSOT system meets these standards and thus stays below the MPE (maximal permissible exposure) limits for skin exposure and is therefore considered safe.

Tissue temperature increases due to MSOT

Optoacoustic imaging does not result in any relevant increase in temperature in the tissue. The absorption of one laser pulse results in a transient local increase in tissue temperature of a few milli-Kelvin. Depending on the duration of the examination and the skin type of the patient, the temperature typically increases by less than one Kelvin.

Histological changes in the tissue

Histological changes in target tissue and surrounding structures are neither to be expected nor have they been observed in previous preclinical or clinical studies.

Slight, reversible reddening or warming of the skin is only to be expected in the case of very sensitive skin.

In case of these rare events, they can be noticed at any time by the study participant or the examining physician; the examination can then immediately be interrupted or aborted. In no case is there irreversible damage to be expected.

In principle, the near-infrared light used in MSOT can lead to retinal damage when the eye is irradiated. To prevent this, study participants and examiners will wear safety goggles at all times during the examination.

Since the data obtained via MSOT will not be used for diagnosis or therapy planning and also not in interpretation of other diagnostic findings, there is no risk of possible misdiagnosis, even if mistakes would occur.

10.2 Benefits associated with the study

The data obtained in the study can provide essential information about the blood circulation and perfusion in muscle of IC patients. It is therefore possible that these diagnostic procedures can be used in the future to better non-invasively detect critical blood flow situations and to derive therapy indications. Especially in groups of patients who can only be assessed inadequately or not at all using classical diagnostic methods.

10.3 Termination criteria

Termination criteria for the individual participant:

Participation in the study is terminated if the skin becomes noticeably warm or reddened. The examination time per anatomical region is limited to three times five minutes, so that these events are very unlikely.

In addition, participation in the study will be discontinued if the exercises between the MSOT measurements which are described above cannot be carried out, e.g. due to dyspnea, orthopedic diseases, etc.

Due to the short duration of study participation, no other termination criteria are provided.

Termination criteria for the entire study:

The entire study must be terminated if previously unknown and unobserved significant and harmful side effects occur through the MSOT examination. This is considered unlikely, as more than 400 patients or volunteers have already been examined with this method at the University Hospital in Erlangen alone.

Otherwise, termination of the entire study is not provided.

10.4 Statement concerning medical responsibility

Based on previous experience with MSOT examinations in adult patients, the risk of adverse events occurring is considered to be extremely low. No central organs are examined in this study, measurements are carried out on the extremities only - this leads to a further significant reduction in a possible residual risk.

11 Results of preliminary study, biometrics

Results of the preliminary study (MSOT_PAD):

In the preliminary study (MSOT_PAD), a total of 59 healthy volunteers and 138 PAD patients in Fontaine stages II, III and IV were examined using MSOT in a very similar study design.

Measurements were taken at rest and after a standardized exercise of a walking distance of 150 meters. For the derivation and validation of meaningful measurement parameters, the study participants were divided into a derivation cohort (31 healthy subjects and 70 PAD patients) and a validation cohort (28 healthy subjects and 68 PAD patients). The presence of angiographic imaging as part of the routine examinations was an inclusion criterion for the participating PAD patients of all PAD stages. The classification of severity of the angiographic images was correlated to the measured hemoglobin-associated MSOT parameters before and after the exercise.

It could be shown that the parameter for oxygenated hemoglobin derived by MSOT correlates with the angiographic severity of the disease and is suitable as a diagnostic biomarker for hemodynamically and clinically relevant arterial occlusions. PAD patients in stages III and IV according to Fontaine could be clearly distinguished from healthy subjects. For patients in the claudication stage (stage II according to Fontaine), however, the differentiability was not satisfactorily sufficient. Here, the present study project hopes for greater accuracy through a more suitable exercise for this patient group between the MSOT measurements.

Statistical methodology:

The data will be displayed as mean values with standard deviation. Correlations will be given using the non-parametric Spearman correlation coefficient (R_s). According to the distribution of the groups, the differences in the mean values are examined statically using a non-parametric test (Wilcoxon test). For all analyses, an error level of <0.05 is considered statistically significant.

12 Data management and data protection

12.1 Data acquisition and storage

All raw data, such as patient files, are source documents. Their availability is ensured for routine monitoring. The participation of the individual patients or healthy volunteers in the study is documented. The study leader keeps an independent list for the identification of the participating persons. This list contains the names and dates of birth as well as the dates of examination and pseudonymization codes of the patients and healthy volunteers. The study leader is responsible for the quality of data collection and storage. The data storage (complete data) takes place on computers or specially designed network drivers of the University Hospital Erlangen.

12.2 Pseudonymization

Prior to a scientific analysis of the materials and data of this study, all information will be pseudonymized according to the guidelines of the Bundesdatenschutzgesetz (Federal Data Protection Act).

12.3 Data transfer

A transfer of the data or biological materials obtained is not intended in this study and will not take place; in particular, the manufacturer of the MSOT device will not have access to the data. The study results can be published anonymously, whereby it will not be possible to draw conclusions about the identity of the participating persons. The data will be kept for ten years and will then be destroyed.

12.4 Revocation, data deletion

If the declaration of consent is revoked, data collected up to this point can be taken into account and can be further stored. However, the patient has the right to request their destruction, unless legal provisions prevent such destruction.

13 Handling of incidental findings in healthy volunteers

All findings including the evaluation of the ABI and the images from the CCDS, are only collected for the purpose of this study and not for the purpose of general or specific diagnostics. Evidence of a disease unknown to the subject may escape detection in these examinations. If abnormal findings are discovered during the scientific evaluation, a specialist will be consulted for the review and evaluation of the data and images originally determined for research purposes. Whether reportable findings are present is decided by the study leader according to his best judgment. The participant will be informed in advance about any disadvantages of getting informed in case of such incidental findings – orally and in the written declaration of consent. Such disadvantages are to be understood as such:

- Strong psychological stress due to the knowledge or suspicion of a threatening disease
- Disadvantages of certain legally significant acts, such as the conclusion of a life or health insurance policy or an employment contract
- Further examinations linked to the findings that may pose a health risk, even if further investigation shows that the original findings had no pathological value

After having been informed about above-mentioned possible disadvantages caused by the information about incidental findings during this study, the participant will give a written declaration whether he/she wishes to be informed about such abnormalities.

14 Handling of biomaterials

No biomaterials are obtained.

15 Insurance

A separate study participant insurance is taken out under an annual contract with the insurer HDI Global SE, Düsseldorf Office. The insurance is based on the agreements in accordance with the „Versicherung für nicht der Versicherungspflicht unterliegende klinische Prüfungen“ („Insurance for clinical trials not subject to obligatory insurance“).

## 1 Version History

Version	Changes	Authors
1.0		[name], [name], [name]

## 2 List of Abbreviations and Definition of Terms

6MWT .....	6 Minute Walk Test
AAA .....	abdominal aortic aneurysm
ABI .....	ankle-brachial index
CCDS .....	color-coded vascular duplexsonography
CFA .....	common femoral artery
CHD .....	coronary heart disease
CHF .....	chronic heart failure
CIA .....	common iliac artery
CKD .....	chronic kidney disease
CLTI .....	chronic limb threatening ischemia
DGA .....	Deutsche Gesellschaft für Angiologie (German Society for Angiology)
EIA .....	external iliac artery
Hb .....	deoxygenated hemoglobin
HbO 2 .....	oxygenated hemoglobin
Hbtot .....	total hemoglobin
IC .....	intermittent claudication
IIA .....	internal iliac artery
MSOT .....	Multispectral Optoacoustic Tomography
PAD .....	peripheral arterial occlusive disease
PSV .....	peak systolic velocity
SFA .....	superficial femoral artery
TASC .....	Trans Atlantic Intersociety Consensus
TS .....	triceps surae muscle

## 3 Introduction

### 3.1 Background

PAD is one of the most common diseases of the elderly. As life expectancy increases, there is a growing need for new treatment concepts and new diagnostic procedures.

Up to now, only the measurement of macrocirculation in the form of CCDS, ABI and the measurement of the actual walking distance are available as independent validation measures of revascularization methods (endovascular/open). The S3 guideline for diagnosis, therapy and medical aftercare of PAD published in 2015 by the DGA recommends such aftercare

examinations, especially for patients that underwent vascular surgery. However, for the mentioned validation measures there are some patient groups for which these methods provide only insufficient or unusable results (e.g. diabetes mellitus, terminal renal failure). In these cases, independent verification of the success of the chosen therapy would have to be performed using angiography (digital subtraction angiography, CT angiography or MR angiography). However, this is not routinely performed in the respective patient populations due to the associated risks (including radiation exposure, contrast agent administration, invasiveness).

MSOT provides a new non-invasive diagnostic method that may be able to fill this diagnostic gap. The technique is based on the photoacoustic effect. Flashes of laser light are sent through the skin into the target tissue. This leads to minimal changes in thermoelastic expansion and contraction of different tissue components or molecules, which causes the emission of ultrasound waves. The same examination unit that sends in the laser flashes can also detect the emitted ultrasound waves. In the newly configured device (Acuity Echo, iThera Medical GmbH, Munich, custom-made, CE-certified), an extended spectrum of laser light can be used, enabling among others the derivation of values corresponding to hemoglobin and its oxygenation levels. As hemoglobin concentration and oxygenation status are markers for perfusion, MSOT-based imaging of these parameters could be a highly sensitive and reliable method to analyze muscle perfusion.

A first study (MSOT\_PAD, NCT04641091) confirmed the hypothesis that data collected via MSOT examination of the calf muscle can be used for PAD diagnostics. The derived concentration of oxygenated hemoglobin (HbO2) proved to be the most suitable measurement parameter. A connection could be established between the measured HbO2 concentration and the clinical stage of PAD. Differentiation improved after a standardized exercise of a walking distance of 150 meters, with patients in the stage of intermittent claudication (IC, Fontaine stage II) being more difficult to differentiate in comparison to patients in Fontaine stages III and IV.

### **3.2 Purpose of the study**

The aim of this cross-sectional study is to increase the sensitivity and specificity of the procedure for IC patients by using a more suitable exercise between first and second MSOT measurement, namely repeated heel raises until the occurrence of claudication pain.

Patients with intermittent claudication are especially interesting to be examined more closely because it could be crucial for early diagnosis, choice of therapy and success monitoring of the therapy to be able to directly examine the circulatory situation of the muscle as the primary target organ. So far, there are no diagnostic options for this. Where previously conservative therapy monitoring was mainly based on anamnesis, MSOT could enable objective control and

evaluation of conservative and interventional/surgical treatment approaches. In the future, this might entail further comparative outcome studies, which might then even result in indication changes for the various therapeutic measures – which would improve the overall care situation of PAD patients.

As additional target variables, the relative, absolute and total walking distance in a 6-minute walk test will be recorded as well as the PAD-specific quality of life (via the VASCUQOL-6 questionnaire).

A healthy control collective is included as a comparison group.

In order to more directly gain insights into a possible monitoring of therapy success, a subgroup of IC patients having been included in the study will be asked to undergo the study protocol a second time after interventional/surgical revascularization and will then be examined again with MSOT.

## **4 Hypothesis, Study Objectives and Endpoints**

### **4.1 Hypothesis to be statistically tested**

The hypothesis is that the MSOT parameters associated with hemoglobin in the calf muscle after a heel raise exercise can predict peripheral artery disease in the intermittent claudication stadium.

H0: The MSOT parameters associated with hemoglobin in the calf muscle after a heel raise exercise do not differ between healthy subjects and patients with PAD in the intermittent claudication stadium.

### **4.2 Objectives**

#### **Primary objectives**

- Study group 1: Derivation of optimal diagnostic thresholds for hemoglobin-associated MSOT parameters after a heel raise exercise in claudication patients and a healthy control group
- Study group 2: Validation of the diagnostic accuracy of MSOT, employing the cut-off values derived in study group 1, regarding hemoglobin-associated MSOT parameters after a heel raise exercise in claudication patients and a healthy control group in an independent cohort

### **Secondary objectives**

- Recording of the reperfusion profiles of the hemoglobin-associated MSOT parameters (i.e. the curves of hemoglobin-associated parameters in the first ten minutes after exercise) and determination of general characteristics of the curves to distinguish between PAD legs and healthy legs
- Recording of the flow profiles and PSVs of the A. femoralis communis and A. poplitea using CCDS and correlation with the collected MSOT parameters
- Recording of the ABI before and after the heel raise exercise and correlation with the collected MSOT parameters
- Recording of the relative (until the first occurrence of pain) and absolute walking distance (until the first stopping due to pain) in the 6MWT and correlation with the collected MSOT parameters
- Recording of the maximum walking distance in the 6MWT and correlation with the collected MSOT parameters
- Recording of the subjectively perceived maximum walking distance in everyday life and correlation with the collected MSOT parameters
- Recording of the perceived PAD-specific quality of life (VASCUQOL-6 questionnaire) and correlation with the collected MSOT parameters
- Recording of the radiological degree of severity and correlation with the collected MSOT parameters  
[If angiographic imaging is already available due to routine diagnostics independently from this study.]
- Subgroup analysis: re-recording of all parameters listed here after revascularization intervention

## **4.3 Endpoints**

### **Primary endpoint**

- Optimal diagnostic thresholds for hemoglobin-associated MSOT parameters before and after a heel raise exercise [Time Frame: single time point (1 day)]: optimal diagnostic thresholds for hemoglobin-associated MSOT parameters in calf muscle tissue in patients with intermittent claudication before and after a heel raise exercise

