5.1 Primary/secondary objectives and hypotheses

Primary hypothesis:

- The quantitative MSOT value for oxygenated hemoglobin in the calf muscle of PAD patients in the claudication stage before and after active exercise until the onset of claudication pain is suitable for distinguishing a diseased from a healthy collective.

Secondary hypotheses:

- The MSOT reperfusion profiles (i.e. the curves of hemoglobin-associated MSOT parameters in the first ten minutes after exercise) of PAD patients in the claudication stage show certain patterns and differ significantly from the reperfusion profiles of healthy subjects.
- The collected MSOT parameters and their reperfusion profiles correlate with the perfusion parameters from the CCDS.
- The collected MSOT parameters and their reperfusion profiles correlate with the ABI.
- The recorded MSOT parameters and their reperfusion profiles correlate with the relative (until the first occurrence of pain) and absolute walking distance (until the first stopping due to pain) of the patient.
- The recorded MSOT parameters and their reperfusion profiles correlate with the total distance reached in the 6-minute walk test.
- The recorded MSOT parameters and their reperfusion profiles correlate with the subjectively perceived maximum walking distance achieved in everyday life.
- The recorded MSOT parameters and their reperfusion profiles correlate with the perceived PAD-specific quality of life (VASCUQOL-6 questionnaire).
- The collected MSOT parameters and their reperfusion profiles correlate with the angiographic severity of the PAD disease.

[If angiographic imaging is already available due to routine diagnostics independently from this study.]

- Subgroup analysis: The MSOT parameters measured again after revascularization intervention show characteristic changes compared to the measurements before intervention
- Subgroup analysis: The MSOT parameters measured again after revascularization intervention show tendencies towards the MSOT parameters of healthy subjects compared to the measurements before intervention
- Subgroup analysis: The reperfusion profiles of MSOT parameters measured again after revascularization intervention show characteristic changes compared to the measurements before intervention

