- Subgroup analysis: The reperfusion profiles of MSOT parameters measured again after revascularization intervention show tendencies towards the reperfusion profiles of healthy subjects compared to the measurements before intervention

Primary objectives:

- Study group 1: Derivation of optimal diagnostic MSOT threshold values regarding oxygenated hemoglobin after exercise in claudication patients and a healthy control group
- Study group 2: Validation of the diagnostic accuracy of MSOT, employing the cut-off values derived in study group 1, regarding oxygenated hemoglobin after exercise in claudication patients and a healthy control group in an independent cohort

Secondary objectives:

- Recording of all other hemoglobin-associated parameters in the calf muscle before and after repetitive heel raises using MSOT
- Recording of the reperfusion profiles (i.e. the curves of hemoglobin-associated parameters in the first ten minutes after exercise) and determination of general characteristics of the curves to distinguish between PAD legs and healthy legs
- Recording of the flow profiles and PSVs of the A. femoralis communis and A. poplitea using CCDS and correlation with the collected MSOT parameters
- Recording of the ABI and correlation with the collected MSOT parameters
- Recording of the relative (until the first occurrence of pain) and absolute walking distance (until the first stopping due to pain) and correlation with the collected MSOT parameters
- Recording of the maximum walking distance in the 6MWT and correlation with the collected MSOT parameters
- Recording of the subjectively perceived maximum walking distance in everyday life and correlation with the collected MSOT parameters
- Recording of the perceived PAD-specific quality of life (VASCUQOL-6 questionnaire) and correlation with the collected MSOT parameters

- Recording of the radiological degree of severity and correlation with the collected MSOT parameters
[If angiographic imaging is already available due to routine diagnostics independently from this study.]
- Subgroup analysis: re-recording of all parameters listed here after revascularization intervention

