5.2 Study type

Monocentric diagnostic cross-sectional study.

6 Target parameters

The measurements with MSOT are each carried out before and after exercise, in the area of the M. triceps surae. MSOT wavelengths are examined in the range from 700 to 1300 nm.

6.1 Primary target:

- Quantitative signal of oxygenated hemoglobin (in arbitrary units)
[This target is measured non-invasively via MSOT.]

6.2 Secondary targets:

- Detection of oxygenated and deoxygenated hemoglobin, total hemoglobin, oxygen saturation and the wavelengths 700 to 1300 nm (in arbitrary units)
[This target is measured non-invasively via MSOT.]
- Recording of the flow profiles and PSVs of the A. femoralis communis and A. poplitea using CCDS
- Registration of the ABI
- Recording of the relative (until the first occurrence of pain) and absolute walking distance (until the first stopping due to pain)
- Recording of the maximum walking distance in the 6-minute walk test
- Recording of the subjectively perceived maximum walking distance in everyday life
- Recording of the currently perceived PAD-specific quality of life (VASCUQOL-6 questionnaire)
- Recording of relevant secondary diseases from the patient file
- Recording of relevant previous operations from the patient file
- Recording of the current medication from the patient file
- Recording of the radiological severity (MRA, CTA, DSA)
[If angiographic imaging is already available due to routine diagnostics and independently of the study described here.]
- Subgroup analysis: re-recording of all parameters listed here after revascularization intervention

7 Study design

Graphic depiction of the study design in Figure 2 on page 13.

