7.2 Study arms: intervention/control

We do not plan any interventions. The study will examine two study groups in series. First, study group 1 will establish thresholds for hemoglobin values using MSOT. Then, in study group 2, the thresholds will be validated and the specificity and sensitivity will be determined. For a subgroup analysis, some of the IC patients having been included in the study will be reexamined after revascularization intervention.

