After the first measurement of the ABI, color-coded duplex sonography (CCDS) of the femoral arteries is performed at rest. The CCDS is used to determine the flow profiles of the examined vessels and allows an assessment of constrictions or occlusions in these vessels. During this examination, the participant remains lying on the examination couch. Depending on the examination conditions (individual anatomy of the vessels, body size, etc.), this examination takes about ten minutes. This examination takes place exclusively for the purpose of this study and is not part of routine diagnostics for patients.

During the 15 minutes of the initial resting phase, the optimal position on the M. triceps surae muscle for the placement of the MSOT probe can already be determined (by means of built-in B-scan sonography). In case of strong hair growth in the examined area above the calf muscle, this area of approx. 5cm x 10cm will be shaved using a medical single-use razor.

After ABI and CCDS the first measurement with the MSOT device is performed over the previously selected position (for patients in the more severely affected leg). The examination is analogous to sonography over the corresponding skin layers without further invasive procedures. The measurement duration per anatomical region is limited to ten minutes; the study participants can remain in a relaxed posture during the examination; assistance in the form of breathing maneuvers or the kind is not necessary.

Following these initial measurements patients are asked to do a heel raise exercise to explicitly exercise the M. triceps surae. The participants should do repeated heel raises until their calf muscles are exhausted. For both IC patients and healthy volunteers this means the occurrence of pain in the calf muscle. All participants will be motivated to continue the heel raises over at least 30 seconds to ensure a minimum exercise time for the muscle. During the exercise the participants should fix themselves with their hands to the wall or door frame for safety.

After the exercise, the participant should lie back down on the examination couch in prone position as quickly as possible and the second measurement of both the ABI and the MSOT parameters after exercise is performed. The MSOT parameters are recorded sequentially every 30 seconds over five minutes and then every minute for another five minutes to possibly record characteristic reperfusion profiles of the muscle after exercise.

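### The SAP gives every haemoglobin-associated MSOT parameter primary status where the protocol names only HbO2 after exercise, and no readable text defines the post-exercise value or fixes it before study group 2 is analysed

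*SAP*

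**What the plan says.** **Protocol.** The first primary objective in 5.1 is "Derivation of optimal diagnostic MSOT threshold values regarding oxygenated hemoglobin after exercise in claudication patients and a healthy control group". The second validates accuracy in study group 2, "employing the cut-off values derived in study group 1, regarding oxygenated hemoglobin after exercise in claudication patients and a healthy control group". Section 6.1 lists the HbO2 signal as the only primary target. The rest is a secondary objective: "Recording of all other hemoglobin-associated parameters in the calf muscle before and after repetitive heel raises using MSOT". The primary hypothesis in 5.1 is also confined to HbO2, but its timing differs from the objectives: the value "before and after active exercise until the onset of claudication pain is suitable for distinguishing a diseased from a healthy collective". Section 7.2 sets the order: "First, study group 1 will establish thresholds for hemoglobin values using MSOT. Then, in study group 2, the thresholds will be validated". Section 9.2 describes the scan after exercise: "The MSOT parameters are recorded sequentially every 30 seconds over five minutes and then every minute for another five minutes".

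**SAP.** The null hypothesis (4.1) and both primary objectives (4.2) concern haemoglobin-associated parameters after exercise, in the plural, without singling out HbO2. The primary endpoint (4.3) is "Optimal diagnostic thresholds for hemoglobin-associated MSOT parameters before and after a heel raise exercise", so pre-exercise values enter here and not in 4.1 or 4.2. Section 5.4 lists HbO2, Hb, total haemoglobin, oxygen saturation and single wavelengths; the tables in section 12 add an HbO2/Hb difference. The opening of section 9 proposes to test both post-exercise readouts and post-minus-pre differences as candidate criteria. Section 9.2 derives a Youden cut-point in study group 1 and applies it in study group 2, without naming the parameter or reading. Section 7.1 keeps the two study groups separate and places the final analysis after the last patient. Section 12.3 gives each parameter one PRE and one POST value, with POST meaning only after exercise.

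**The concern.** The two documents define different primary results. Parameters that are secondary in the protocol share primary status in the SAP, and nothing says which of them decides whether the validation succeeded. Two analysts following these documents could validate different primary results in good faith.

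The POST value has the same weakness. A cut-point cannot be reproduced without knowing which reading, or which summary of the readings, it cuts. The sample size re-evaluation after 25 patients and 25 healthy volunteers (SAP 6) names no parameter either.

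What is at stake is the study group 2 conclusion. Comparing candidates in study group 1 does no harm if one parameter, one reading and one cut-off then go forward. If the choice remains open once study group 2 data are visible, the validation cohort no longer gives an unbiased check.

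**Working it through.** Below, a cell is one of the four sets sized in SAP 6 (patients or healthy volunteers, study group 1 or 2).

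**1. The texts side by side**

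| Item | Protocol | SAP |
|---|---|---|
| Primary parameter | HbO2 (5.1, 6.1) | all haemoglobin-associated parameters (4.1–4.3) |
| Timing | after (5.1 objectives); before and after (5.1 hypothesis) | after (4.1, 4.2); before and after (4.3) |
| Other haemoglobin parameters | secondary (5.1, 6.2) | within the primary |
| Post-minus-pre difference | not in the primary | secondary in 4.3; candidate criterion in 9 |

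**2. Number of candidates.** SAP 5.4 without wavelengths gives 4 parameters. Adding PRE values, as only SAP 4.3 does, gives 4 × 2 = 8. Readings after exercise under Protocol 9.2: 10 (every 30 s for 5 min) + 5 (every minute for 5 min) = 15 per parameter.

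**3. The plan's own sample size.** Inputs from SAP 6: AUC 0.7, significance level 0.05, power 0.8. Assumed, because not stated: null AUC 0.5, two-sided test. With the Obuchowski binormal variance at 1:1:

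- A = 1.414 × z(0.7) = 0.7415, so A² = 0.550
- V = 0.0099 × exp(−A²/2) × [(5A² + 8) + (A² + 8)] = 0.145; null variance V0 = 0.0099 × 16 = 0.1584
- n = [1.96 × √0.1584 + 0.8416 × √0.145]² / 0.2² = (0.780 + 0.321)² / 0.04 = 30.3, rounded up to 31

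This is the plan's figure, and 4 × 31 = 124 is its maximum. One-sided versions give 24 to 26 and do not match. Power is 0.81 at 31 per cell and 0.72 at 25 per cell (100 / 4, from the approximate total in SAP 5.2). The 31 therefore carries no allowance for several primary parameters. With Bonferroni, the same formula needs 44 per cell for four candidates and 50 for eight.

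**4. False positives within one study group, no true effect.** Independent tests give upper figures: 1 − 0.95⁴ = 18.5% and 1 − 0.95⁸ = 33.7%. The parameters are not independent, so their structure was simulated: HbO2 and Hb lognormal (log SD 0.4), total = HbO2 + Hb, saturation = HbO2 / total, Hb–HbO2 correlation 0, 0.4 or 0.8, pre–post correlation 0, 0.5 or 0.8, Mann–Whitney test, 31 per cell, 20,000 runs. The documents give none of these spreads or correlations; they are assumptions.

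| Quantity | 4 parameters | 8 (PRE and POST) |
|---|---|---|
| At least one p<0.05 in one study group | 11.7–14.5% | 18.1–26.1% |
| Any success in study group 2, same direction as study group 1 | 6.4–7.9% | 11.2–14.7% |
| Mean Youden index in study group 2, best-of rule (3,000 runs) | 0.098–0.106 | 0.146–0.155 |

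With the study group 1 winner locked, the same-direction rate in study group 2 is 2.3–2.8% and the mean Youden index lies between −0.003 and 0.003. The last two rows of the table apply only under an any-success or best-of rule, which neither document states.

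**5. Open choice among 15 readings of one parameter.** Equal correlation between readings, assumed 0.9 to 0.7: at least one p<0.05 in one study group, 15.5% to 27.5%; in study group 2 if any reading may count, 9.7% to 16.3%; locked, 2.5% to 2.3%.

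**The case against.** The strongest reply is that the plan already protects the validation. The study groups are examined in sequence, handled separately, and the study group 1 cut-point is carried over. A cut-point in arbitrary units means nothing apart from the variable it came from, so carrying it forward largely carries the parameter and reading too. SAP 9.2 reports sensitivity and specificity with confidence intervals and sets no success criterion, SAP 12.5 tabulates every parameter, and the protocol calls the study exploratory. On this view the group 2 error rates describe rules the plan does not contain.

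Much of that stands. No passage says selection continues in study group 2, and full tabulation is not a best-of rule. But with several parameters there are several cut-points, and nothing says which one carries the conclusion. SAP 7.1 states no lock. The exploratory label sits beside a stated null hypothesis and a powered sample size.

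Two narrower points are fair. The opening of SAP 9 tests post-exercise readouts and differences rather than PRE values alone, so eight follows the SAP 4.3 wording; four readouts plus four differences give a similar 20–26%. And the sample size shows no multiplicity allowance, but it does not itself name HbO2.

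On POST, Protocol 9.2 treats the scan after exercise as the second measurement and SAP 4.3 makes the ten-minute curve a separate secondary endpoint. That narrows POST without defining it. Two figures are not shown, so this point is limited to readable text.

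**Conclusion.** The concern holds. The conflict over the primary parameter is in the wording and rests on no simulation: the protocol has one primary parameter, while the SAP has at least four and states no rule for choosing among them. The undefined POST value is a second gap, subject to the figures that cannot be read.

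The calculations show what the open choice could cost. Under the assumed correlations, unadjusted testing within a study group roughly doubles or triples the nominal 5% for four parameters and multiplies it by about four to five for eight. In study group 2 the cost is conditional: if any candidate may count, the same-direction rate rises from about 2.5% to between 6.4% and 14.7%; if the best is picked, a useless test would show a mean Youden index of about 0.10 to 0.16. With the choice fixed after study group 1, both effects vanish. This should be fixed before study group 2 is analysed.

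**What to change.** - **SAP 4.1–4.3 and 9.2:** name HbO2 after exercise as the sole primary parameter, as in the Protocol 5.1 objectives and 6.1. Label the other parameters, PRE values, differences and single wavelengths secondary or exploratory, and align the opening of SAP 9.
- **Protocol 5.1:** reconcile the timing in the primary hypothesis with the primary objectives.
- **SAP 9.2 and 12.3:** define POST as one pre-specified reading or one summary of the readings, chosen by the sponsor.
- **SAP 7.1:** state that parameter, reading and Youden cut-off are fixed from study group 1 before any study group 2 MSOT data are analysed.
- **SAP 6:** state that the re-evaluation after 25 + 25 participants uses the same parameter and reading.

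The cost is SAP wording and one protocol sentence. The fix adds no participants, since 31 per cell is the plan's own figure for one AUC; whether about 25 or 31 per cell is recruited stays with the planned re-evaluation. All other parameters are still reported, but they cannot carry the primary conclusion. Keeping four or eight co-primaries with Bonferroni would instead need 4 × 44 = 176 or 4 × 50 = 200 participants, against the planned maximum of 124.
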